7 SAFETY MANAGEMENT

7.1 Clinical Adverse Events

Clinical adverse events (AEs) will be monitored throughout the study.

7.2 Adverse Event Reporting

Since the study procedures are not greater than minimal risk, SAEs are not expected. If any unanticipated problems related to the research involving risks to subjects or others happen during the course of this study (including SAEs) they will be reported to the IRB in accordance with CHOP IRB SOP 408: Unanticipated Problems Involving Risks to Subjects. AEs that are not serious but that are notable and could involve risks to subjects will be summarized in narrative or other format and submitted to the IRB at the time of continuing review.

For students enrolled in the treatment sessions: Careful baseline screening will be conducted to identify participants whose risk for potential adverse effects are elevated were they to utilize the study treatment. If a participant becomes more symptomatic (based on parent/child report or agency/clinician judgment), the STS provider will review the participant's clinical status with the project team and PI. Concerns about deterioration will trigger an evaluation by the STS Therapist and then discussion with the PI regarding whether discontinuation from the study is in the best interest of the student. Such participants will be removed from the study and treated openly with appropriate clinical care.

In the event that suicidality is noted during the course of the eligibility evaluation or during participation in the study, CHOP evaluator will communicate finding to STS therapist to ensure that this information is incorporated into their standard care of practice. CHOP evaluator will also inform on-call CHOP-based licensed clinical provider to ensure any other potential safety measures that may need to be put in place to provide appropriate care, including but not limited to informing parents, STS staff, and other professionals involved with the child's mental health care. If CHOP staff learns or observes of any changes in a child's mental health status that would affect their eligibility status while participating in treatment groups, the child may be withdrawn from the study at the discretion of the PI. All eligibility decisions will be made in collaboration with the STS team.

The procedures of reporting adverse events include immediately notifying their supervisor and the PI and following procedures to maintain participant safety. Study therapists will have the PI's cell phone number and beeper or cell phone contact information for their clinical supervisor. Children and guardians will also be given emergency contact information should they require assistance or in the case of an emergency.

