4.4 Subject Completion/Withdrawal

Subjects may withdraw from the study at any time without prejudice to their care, education or employment. They may also be discontinued from the study at the discretion of the Investigator for lack of adherence to the study and/or development of exclusionary criteria. Student participants will be removed from the study if they develop exclusionary criteria during the trial (e.g. Bipolar Disorder I, acute suicidality, psychotic symptoms, etc) or if it is determined that the intervention group is not age/developmentally appropriate based on the grade level of the majority of enrolled students. As examples, acutely suicidal participants would be excluded from study participation, as would participants who require medical attention for a severe medical illness. It will be documented whether or not each subject completes the clinical study. If the Investigator becomes aware of any serious, related adverse events after the subject completes or withdraws from the study, they will be recorded in the study files.

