6.1 Primary Endpoint

Effectiveness between treatment groups (FRIENDS and CATS) will be tested by calculating the 95% confidence limits (the width of the limit =|4.20|) for the differences in symptom severity, impairment, and academic competence (child outcomes) from pre to post between children receiving FRIENDS and children receiving CATS. If the calculated differences are within the 95% limit, then we will conclude that the two interventions have an equal impact or effect on child outcomes. If any of the differences in child outcomes is/are larger than the upper limit, then we will conclude that one intervention is better than the other. The limit of |4.20| was chosen based on the distribution of the reported mean effect sizes associate with FRIENDS.

Qualitative interviews with supervisors and therapists (perceived acceptability of support strategies) will be audio-recorded, transcribed and entered into NVivo 10.0 for coding and analysis. For each interview, a codebook (of common themes related to the appropriateness and acceptability of the support they received) will be developed and trialed by three coders based on an initial reading of the transcripts, and revised through discussions and subsequent transcript reviews. Coders will meet regularly to compare coding and revise the codebook. This will yield a stable set of qualitative codes that will be used to code the transcripts. Two independent coders will then code all of the transcripts. This iterative process will be continued until consensus is reached and saturation occurs. Coder reliability will be checked quarterly using the inter-rater reliability function in NVivo.

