6.3 Sample Size and Power

Number of students and statistical power. It is anticipated that a total of 284 (142 students per treatment protocol) will complete the proposed study. The published reported effect size of FRIENDS has been estimated to equal 0.56 (cohen's *d*). In testing for equivalence of FRIENDS and CATS, using two one-sided tests with sample sizes of 142 in FRIENDS and 142 in CATS achieves 88% power at a 5% significance level when the true difference between the means is 0 (null hypothesis), the standard deviation of the differences in means is assumed to be 11, and the equivalence limits are -4.20 and 4.20.

Number of therapist and statistical power. To compare TT to TT+ for the implementation of CATS (H2a), with 30 therapists in TT and 30 in TT+ achieve 86% power to detect a

difference of 8% between the null hypothesis that both group means are 80% (content fidelity) and the alternative hypothesis that the mean of group TT is 80% with estimated group standard deviations of 10 and 10 (an estimated effect size=.8) and with a significance level (alpha) of 0.05 using a two-sided two-sample t-test. Similarly, group sample sizes of 30 and 30 achieve 84% power to detect a difference of 0.7 in process fidelity between the null hypothesis that both group means are 4 and the alternative hypothesis that the mean of group TT+ is 4.7 with estimated groups standard deviations of 0.9 and 0.9 (an estimated ES= .78) and with a significance level (alpha) of 0.05 using a two-sided two-sample t-test.

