or, if deterioration is noted during treatment (based on self-report, parent-, child-, teacher-report or clinical judgment), or if a family is interested in further treatment, we will work with them to identify appropriate referrals. This will include the option to work with a clinician, either at the Department of Child and Adolescent Psychiatry and Behavioral Sciences (DCAPBS) of the Children's Hospital of Philadelphia or at Child & Adolescent OCD, Tic, Trich & Anxiety Group (COTTAGe) at the University of Pennsylvania, Department of Psychiatry. Participants may experience at least some subjective distress during treatment, and their reactions will be closely monitored and addressed therapeutically. In the unlikely event that a child manifests unusually high levels of distress, suggesting prohibitive side effects or intolerance of treatment, he or she will be withdrawn from the study by the PI and clinical recommendations in the best interest of the child will be made on a case by case basis. Inperson parent meetings will be scheduled as needed should clinical need arise (e.g., address clinical worsening, address parent concerns, prevent premature termination).

Potential Risks to STS Therapists and Clinical Supervisors. There are no known physical or legal risks for STS therapists and clinical supervisors to participating in the study. One potential risk might be related to the video recording of treatment and supervision sessions. Therapists might be apprehensive about being video-recorded while conducting treatment sessions with children and therapists and supervisors might feel apprehension about being video-recorded while participating in supervision. In a current study we are conducting, school-based therapists did not object to and did not report any apprehension about being video recorded while conducting groups and receiving consultation from members of the research group. Supervisors and therapists will be told that the video-recordings will be used for research purposes only and that they will not be shared with agency or school administrators. If a therapist or supervisor raises strong concerns about being video recorded either before or after consenting to participate in the study, we will not insist on having them participate or allow them to drop out of the study.

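### Deterioration, and removal because of it, is never compared by arm, so the equivalence conclusion in 6.1 can rest on completers and omit the children who did worst

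*Combined protocol and SAP*

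**What the plan says.** Section 6 covers child outcomes, fidelity, interviews, costs and power. For child outcomes, 6.1 sets the FRIENDS-CATS difference in pre-to-post change against limits of ±4.20: "If the calculated differences are within the 95% limit, then we will conclude that the two interventions have an equal impact or effect on child" (that is, child outcomes). The opening of section 6 adds means, medians, ranges and standard deviations by time point and group, and leaves a Mann-Whitney test on change as an option. Worsening is not defined, and no count of worsened children, removals or adverse events is planned by arm.

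Harm is handled elsewhere, as reporting and individual care:

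- **7.1** is one sentence: "Clinical adverse events (AEs) will be monitored throughout the study".
- **7.2** sends serious and unanticipated problems to the IRB by a separate route. For the rest: "AEs that are not serious but that are notable and could involve risks to subjects will be summarized in narrative or other format and submitted". The recipient is the IRB, at continuing review.
- **8.4.1** has every adverse event reported at once to three IRBs and to NIMH. For non-serious events this timing does not match 7.2, and the two passages must be reconciled.
- **7.2** also says that concern about deterioration leads to an evaluation and a discussion of discontinuation, and that such participants are then removed and treated openly.
- **8.4.2** provides for referral "if deterioration is noted during treatment (based on self-report, parent-, child-, teacher-report or clinical judgment"), and for withdrawal in the event, described as unlikely, of unusually high distress.
- **4.4** states: "It will be documented whether or not each subject completes the clinical study". It does not ask for the reason.
- **3.2.1** places the post-treatment assessment after the 12 or 8 sessions are completed.

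**The concern.** CATS is an adapted, shorter form of FRIENDS (8 sessions against 12), and 1.4 itself warns that adaptation can make a treatment less effective. A conclusion of equality would support using CATS in place of FRIENDS.

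The removal rule and the timing of the post-treatment assessment work together. A child who deteriorates and is removed has no planned post score, and section 6 gives no rule for a missing one. The sample size in 6.3 is stated for students who complete. If more children are removed from one arm than from the other, the comparison of change is made on a selected group, and no table by arm would show it. Reports to the IRBs and NIMH protect the individual child, but they do not give the reader of the trial a comparison.

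**Working it through.** **Inputs from 6.3.** The test is specified "using two one-sided tests with sample sizes of 142 in FRIENDS and 142 in CATS"; it "achieves 88% power at a 5% significance level when the true difference between the means is 0"; "the standard deviation of the differences in means is assumed to be 11, and the equivalence limits are -4.20 and 4.20". The effect size for FRIENDS is d = 0.56. Section 3.2.2 expects 360 students, so three equal arms would have 360/3 = 120 each.

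**Assumptions, not in the documents.** The SD of 11 is the SD of individual change, change is normal, and d converts to a mean improvement of 0.56 × 11 = 6.16 points. The documents give no rate of deterioration or removal.

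**1. Reproduce the stated power.** SE = 11 × √(2/142) = 1.305. Power = 2Φ(4.20/1.305 − 1.645) − 1 = 0.884, which matches the stated 88%. The largest observed difference that still passes is 4.20 − 1.645 × 1.305 = 2.05 points.

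**2. Effect of removal.** Suppose a fraction f of CATS children worsen by 11 points on average and are removed without a post score. Suppose also that no FRIENDS child is removed and that all other children in both arms improve by 6.16 on average. The completers' difference is then 0. The difference over all children is f × (11 + 6.16) = 17.16f:

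| f | true CATS disadvantage | difference among completers |
|---|---|---|
| 10% | 1.7 | 0 |
| 15% | 2.6 | 0 |
| 20% | 3.4 | 0 |

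At 15% and 20% the hidden disadvantage exceeds the 2.05 points that would still pass; at 10% it does not. If the same fraction with the same worsening were removed in both arms, nothing would be masked.

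**3. Can more children worsen while equivalence is declared, without any removals?** Two cases at 142 per group:

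- CATS truly 2.0 points worse, SD 11. The share whose score rises is Φ(−6.16/11) = 28.8% under FRIENDS and Φ(−4.16/11) = 35.3% under CATS, an excess of 6.5 points. Equivalence is declared with probability 0.515.
- Equal means, CATS SD 14 (assumed). The share worse by more than 4.20 points is Φ(−10.36/11) = 17.3% against Φ(−10.36/14) = 23.0%, an excess of 5.7 points. Equivalence is declared with probability 0.756.

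With identical distributions and no selective removal, the shares are equal.

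**4. Precision of a count by arm.** Half-width = 1.96 × √[p₁(1−p₁)/n + p₂(1−p₂)/n]. For the two cases in step 3 this is 10.8 and 9.3 points at n = 142. Multiplying by √(142/120) = 1.088 gives 11.8 and 10.1 points at n = 120. For rarer events, such as removals, it is smaller: at n = 142, 6.1 points for 5% against 10%, and 8.2 points for 10% against 20% (assumed rates). All of these ignore clustering by school, which widens them; the documents give no intraclass correlation.

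**The case against.** The strongest reply is that this is a minimal-risk comparison of two active programmes with weekly safety meetings and reporting to three IRBs and NIMH, and that the proposed table cannot resolve the differences at issue. Much of that stands. The excesses of 5.7 and 6.5 points in step 3 lie inside their own half-widths of 9.3 and 10.8 points, so the table can describe worsening but not test it. It also does not settle how 6.1 should treat missing post scores, which is a separate question.

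A reader might infer four stronger things that the documents do not support:

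- **That worsening is a known harm of these treatments.** In 8.4.2 the item labelled a risk is lack of effect. Deterioration and distress appear there and in 7.2 as contingencies, and no observed harm is reported.
- **That all adverse events become narratives.** The sentence in 7.2 concerns non-serious events and allows other formats.
- **That outcomes are compared only as means.** Standard deviations, ranges and possibly a Mann-Whitney test are also planned. Standard deviations by group could hint at a wider spread under CATS, but none of these gives a rate of worsening.
- **That a 14-point excess could readily pass as equal.** That figure, Φ(−1.96/11) = 42.9% against 28.8%, arises only at a true difference of 4.20, where equivalence is declared 5% of the time.

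What the reply does not meet is the removal problem: reporting to IRBs does not put removed children back into any comparison between arms.

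**Conclusion.** The point holds as a gap in analysis and reporting. Followed as written, the plan has no comparison by arm of deterioration, of removal because of it, or of adverse events. Because removed children have no planned post score, the equality conclusion can omit those who did worst. On the assumed figures, 10% to 20% selective removal from CATS hides 1.7 to 3.4 points against a margin of 4.20.

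The size rests on assumed removal rates, an assumed 11-point worsening, removal in one arm only, and reading d = 0.56 as 6.16 points. It shows what can happen, not what will. The documents do not say that removed children will be excluded from the analysis; they make no provision for measuring or handling them. The primary analysis can still be run, so this is a cheap improvement and not a fault that invalidates the design.

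**What to change.** Add a short subsection to section 6 on descriptive safety reporting, for arms A, B and C separately:

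1. The number and proportion of students removed or withdrawn for deterioration, distress or acute risk, counted whether or not a post score exists.
2. The number and proportion whose score on one named scale and informant (for example MASC-2 Total, child form) worsens by more than a threshold fixed before analysis. One scale and one informant avoid the inflation by chance of an any-scale rule.
3. All recorded adverse events.

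Give the A-B and B-C differences with 95% confidence intervals that allow for clustering by school, and report them beside the equivalence statement in 6.1. Reconcile the adverse-event timings in 7.2 and 8.4.1.

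The cost is one paragraph and one or two tables, with no new visits or measures. The reason for each removal must be recorded, since 4.4 asks only whether each subject completes. The intervals will be wide, particularly with about 120 or fewer students per arm and clustering, so the tables should be labelled descriptive. No change to clinical handling is proposed.

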3.2 Study Duration, Enrollment and Number of Sites

3.2.1 Duration of Study Participation

Agency Supervisors: There is no time limit placed on the duration of participation for agency supervisors. They may continue working with the research team for the duration of the study (5 years) or as long as their agency remains involved in the study or as long as they remain employed by the participating agency.

Agency (STS) Therapists Implementing EBP Interventions: Therapists are asked to commit to participate in the study for one school year. After the initial year, the study team would prefer to train a new therapist in an effort to minimize the effects of differences in therapist experience and therapist dropout on outcomes (yearly therapist dropout in the agencies is 25%). However, based on agency need and staff consideration, therapists can participate in additional years at the study team's discretion. This will be determined on a case-by-case situation. Therapists will be free to continue to implement the intervention groups outside the research project after participation in the study has concluded.

Students: Students who are determined to be eligible, based on the SCARED, and for whom consent/assent is obtained, will participate in a 30 minute baseline data collection session and then in the intervention which will consist of 12 (FRIENDS) or 8 (CATS) 40 minute (or one-class period) intervention sessions, conducted at school. They will also participate in a similar post-treatment data collection session once the intervention (12 or 8 sessions) is completed. Parents of the students participating in the intervention will also participate in two 30-minute data collection sessions (completion of the CBCL, CDI, and MASC-2, see section 5.2 below).

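### Students can be removed from the study for worsening, with no post-treatment assessment or missing-data rule for them, which can bias the FRIENDS–CATS equivalence test

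*Combined protocol and SAP*

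**What the plan says.** Three places in the combined protocol and SAP take students out of the study, not only out of the treatment group, for reasons linked to worsening or distress:

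- Section 7.2 (Adverse Event Reporting): concern about deterioration leads to an evaluation by the therapist and then "discussion with the PI regarding whether discontinuation from the study is in the best interest of the student". The text continues: "Such participants will be removed from the study and treated openly with appropriate clinical care". The next paragraph, on changes in mental health that affect eligibility, is softer: "the child may be withdrawn from the study at the discretion of the PI".
- Section 4.4 (Subject Completion/Withdrawal): "Student participants will be removed from the study if they develop exclusionary criteria during the trial".
- Section 8.4.2 (Risk Assessment): for unusually high distress, "he or she will be withdrawn from the study by the PI". For deterioration, the same section says only "we will work with them to identify appropriate referrals".

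Section 3.2.1 gives each student a "post-treatment data collection session once the intervention (12 or 8 sessions) is completed". No section provides for assessing a student who leaves before that point.

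Section 6.1 compares FRIENDS and CATS on pre-to-post change, and symptom severity is one of the outcomes. Section 6.3 powers an equivalence test (two one-sided tests, limits ±4.20) on the expectation that "a total of 284 (142 students per treatment protocol) will complete the proposed study". Section 6 states no analysis population, no missing-data method and no sensitivity analysis. A textbook on missing data is in the reference list, but the text applies no method from it.

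**The concern.** Removal for worsening depends on something close to the primary outcome. If removed students have no post-treatment score, the missing scores come mainly from the bad end of the distribution. Suppose one program works less well and the same practice applies in both arms. More of its students leave, its remaining mean looks better, and the spread of scores narrows. Both effects make equivalence easier to declare.

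Removal may also differ between arms. FRIENDS has 12 sessions in which worsening can be noticed and CATS has 8, so the error could run either way. Scores that were never collected cannot be recovered at the analysis stage.

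**Working it through.** **Inputs from section 6.3:** 142 per arm, SD 11, limits ±4.20, 5% level, published FRIENDS effect size 0.56.

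**Assumptions:**
- Change is post minus pre, and positive means worse.
- FRIENDS mean change is −0.56 × 11 = −6.16.
- CATS is truly 4.20 worse, so its mean is −6.16 + 4.20 = −1.96.
- 142 per arm are analysed, students are independent (as in the plan's own calculation), and the normal approximation holds.
- All removal rules below are invented, because the documents give no rate.

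**1. The plan's figure.** SE = 11 × √(2/142) = 1.305, and 4.20/1.305 = 3.217. Power at zero difference = 2Φ(3.217 − 1.645) − 1 = 88.4%, which reproduces the stated 88%. At a true difference of 4.20, the chance of declaring equivalence is Φ(−1.645) = 5.0%. With full post-treatment data, both figures stand.

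**2. Same rule in both arms, removal driven by the outcome score.** A student whose change exceeds c is removed with probability p. For an arm with mean μ, let a = (c − μ)/11 and q = 1 − Φ(a).

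- Fraction removed = pq
- Remaining mean = μ − 11pφ(a)/(1 − pq)
- Remaining variance = 121 × {[1 − p(q + aφ(a))]/(1 − pq) − [pφ(a)/(1 − pq)]²}
- False equivalence ≈ Φ((4.20 − d)/SE − 1.645), where d is the expected observed difference

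Worked case, c = 15 and p = 1:
- FRIENDS: a = 1.924, q = 0.027, mean −6.87, SD 10.27.
- CATS: a = 1.542, q = 0.062, mean −3.38, SD 9.74.
- d = 3.48 and SE = √((10.27² + 9.74²)/142) = 1.188.
- False equivalence = Φ(0.60 − 1.645) ≈ 15%.

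| Students removed | FRIENDS / CATS removed | Observed difference | False equivalence |
|---|---|---|---|
| none | 0 / 0 | 4.20 | 5% |
| half of those above 15 | 1.4% / 3.1% | 3.86 | 8% |
| all above 15 | 2.7% / 6.2% | 3.48 | 15% |
| half of those above 10 | 3.5% / 6.9% | 3.67 | 11% |
| all above 10 | 7.1% / 13.9% | 2.99 | 29% |

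If 142 is the number before removal, the last figure becomes 27%.

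**3. Same rule, removal driven by a judgment only correlated with the score.** Let ρ be the correlation between the judgment and outcome change. Set the threshold so that 3% of FRIENDS students are removed (a = 1.881), and for CATS a = 1.881 − ρ × 4.20/11. Then the remaining mean = μ − 11ρφ(a)/Φ(a), and the remaining SD = 11 × √(1 − ρ²[aφ(a)/Φ(a) + (φ(a)/Φ(a))²]).

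| ρ | Observed difference | False equivalence |
|---|---|---|
| 1 | 3.44 | 16% |
| 0.7 | 3.86 | 9% |
| 0.5 | 4.03 | 6.5% |
| 0.3 | 4.14 | 5.5% |

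With 7% of FRIENDS removed and ρ = 0.5, false equivalence is about 8%. If the judgment differs between programs by the full 4.20/11 = 0.38 SD instead of ρ times that, 7% removal gives about 9% to 17% for ρ from 0.3 to 0.7.

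**4. Unequal removal.** Take c = 5, with p = 0.5 in FRIENDS and 0.25 in CATS.

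| True CATS − FRIENDS | Observed | Declared equivalent |
|---|---|---|
| +4.20 (CATS worse) | 4.66 | 2.2% |
| 0 | 0.74 | 87% |
| −4.20 (CATS better) | −3.20 | 20% |

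With a true difference of 0 and the same rule in both arms, the expected difference stays 0 and only the SD narrows.

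**The case against.** The strongest reply has four parts.

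- **Loss of scores is nowhere stated.** A reader might infer that the plan discards the post-treatment scores of removed students. The documents do not say so. They are silent, and the inference rests on that silence plus the timing rule in 3.2.1. Powering on expected completers is ordinary attrition planning and does not define who is analysed. This stands, so the point is that no assessment is provided for, not that one is forbidden.
- **Removal is not automatic.** Section 7.2 puts evaluation and discussion first, and its removal sentence can be read as covering only students for whom discontinuation is chosen. Section 8.4.2 answers deterioration with referrals and calls withdrawal for distress unlikely. The examples in 4.4 (such as acute suicidality) are not worsening on an anxiety scale. This also stands, and it argues for low removal and for a ρ below 1.
- **The direction is not fixed.** A reader might infer that the bias must favour equivalence. That needs a true difference and similar removal in both arms, and step 4 shows a case that goes the other way.
- **Completion is already documented.** Section 4.4 requires a record of whether each subject completes, so removals could be counted by arm. That covers the count but not the missing scores.

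None of this supplies a post-treatment score for a removed student or a rule for analysing without one.

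**Conclusion.** The concern holds in a limited form. As written, the plan allows outcome-related removal from the study, schedules the post-treatment assessment only after the last session, and has no analysis population or missing-data method for an equivalence claim. Missing scores would be informative and can bias the FRIENDS–CATS comparison.

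The size is unknown. With CATS truly at the 4.20 limit, and about 1–7% of FRIENDS and 3–14% of CATS students removed, false equivalence lies between roughly the nominal 5% (removal weakly related to the score) and about 15–29% (every student above a cut-off on the score removed). The upper figures assume that clinical judgment coincides with the outcome scale, which the documents do not suggest. They are the high end of an assumed range, not a forecast. If removal differs by arm, the bias can instead enlarge a difference or create one.

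Sections 7.2 and 8.4.2 also differ on what deterioration leads to and must be reconciled. The change is worth making because it is cheap and the lost data cannot be rebuilt.

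**What to change.** Leave every clinical decision as it is. Then:

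1. Reconcile the wording of 7.2 and 8.4.2 on what follows deterioration.
2. In 4.4, 7.2 and 8.4.2, distinguish leaving the treatment group from leaving the study.
3. Seek the planned post-treatment measures, with parent consent and student assent, from students taken out of the group, and state the timing in 3.2.1.
4. In section 6, analyse all students in their assigned arm and report removals by arm and reason.
5. Add a sensitivity analysis of the equivalence test that allows scores to be missing not at random, such as a delta-adjusted or tipping-point analysis with separate shifts by arm.

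The cost is a short amendment and a few extra questionnaire sessions of about 30 minutes each. Some families will decline, so step 5 is needed even if step 3 works well.
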